# 4.5 End of treatment period visit/ Early Termination or Rescue (Visit 5, Week 24)

Visit 5 (End of Treatment Visit) should occur 12 weeks after Visit 4 or if the patient discontinued early from IP or is rescued. Prior to this visit, patients are required to have fasted overnight (8 to12 hours). Patients are advised to refrain from alcohol intake and intense exercise 24 hours prior to each visit and recommend not to use tobacco/nicotine within 12 hours prior to each visit. Patients should delay administering the morning dose of metformin and study medication on the morning of the visit and bring metformin and study medication to the study site visit.

# All patients who are rescued or who discontinue study drug should remain in the study and follow the visit schedule.

The following procedures will be conducted:

- 1. A complete physical examination may be conducted at Investigators discretion (see Section 5.2.2).
- 2. Vital signs (sitting systolic and diastolic BP and Heart Rate) will be measured (see Section 5.2.3).
- 3. Body weight will be measured Section 5.1.3.
- 4. BMI will be calculated.
- 5. Concomitant medications (including over the counter and herbal/nutritional supplements) will be reviewed.
- 6. Blood samples will be collected prior to administration of study medication for the following assessments:
  - Clinical chemistry (see Section 5.2.1)
  - Hematology (see Section 5.2.1)
  - HbA1c

- eGFR (MDRD)
- FPG (samples for central laboratory testing, see Section 5.2.1)

#### CC

- 7. Urine will be collected for urinalysis.
- 8. AEs and SAEs will be reviewed.
- 9. Patient diary will be reviewed for glucometer values and/or hypoglycaemic events history.
- 10. Diet and Exercise counseling will be provided.
- 11. Study medication compliance will be reviewed.
- 12. Patient diary will be collected (not applicable for rescue visit, for end of treatment only).
- 13. Study medication will be returned (not applicable for rescue visit).
- 14. Glucose meter and/or supplies and instructions will be collected.

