#### 3.9.4 Procedures for discontinuation of a patient from investigational product

At any time, patients are free to discontinue IP or withdraw from the study (i.e., IP and assessments – see Section 3.10), without prejudice to further treatment. A patient who decides to discontinue IP will always be asked about the reason(s) and the presence of any AEs. If possible, the patient will be seen and assessed by an Investigator. Any AEs will be followed up (see Section 6.3.5); patient diaries and all study drugs should be returned by the patient.

Patients who discontinue from the study medication will have an Early Termination Visit equivalent to the Visit 5 (Week 24/End of Treatment) assessments immediately following discontinuation of study medication (see Section 4.5).

If a patient is discontinued from the study, his/her randomisation or enrolment number will not be reused, and the patient will not be allowed to re-enter the study. Randomised patients who discontinue early from the study will not be replaced.

All patients who discontinue study drug should remain in the study and follow the original visit schedule. Patients unable or unwilling to return for scheduled visits will have the opportunity to receive follow-up via telephone calls placed by the site mainly to review safety and concomitant medications. The only exception to this procedure is when a patient withdraws consent for all study procedures or loses the ability to consent freely (i.e., is imprisoned or involuntarily incarcerated for the treatment of either a psychiatric or physical illness).

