## Table 1 Study Plan

Evaluation	Screeni ng a Non- fasting	Enrolm ent Fasting	Tre Peri Fast		nt	End of Treatment / Early Termination/ Rescue Fasting		
Visit	0	1 c	2 d	3	4	5	Notes	
Week	-3	-2	0	6	12	24		
Relative to Randomisation (days) e	-21	-14	R	42	84	168		
Visit window (days)		+3	±3	±7	±7	±7		
							to Appendix E)	
Hepatitis Screening Panel, TSH		X					Section 5.2.1	
Other								
Dispense patient diary		X	X	X	X		Section 5.3.1	
Dispense glucometer and/or supplies/instructions		X	X	X	X		Section 5.3.1	
Dispense study medication			X		X		Section 7	
Return study medication k					X	X	Section 4.5	
Study Medication Compliance Review				X	X	X	Section 7.6	
Dispense open label rescue medication (if necessary)				X	X		Section 4.4	

Abbreviations: AE adverse event, BP blood pressure, BMI body mass index, E-code enrolment code, eGFR estimated glomerular filtration rate, FPG fasting plasma glucose, HbA1c haemoglobin A1c, R randomisation, SAE serious adverse event, WOCBP women of child-bearing potential, EOT end of treatment.

- a Screening visit (Visit 0) will occur 1 week prior to Enrolment (Visit 1) to screen for eligibility based on a non-fasting sample of HbA1c (assessed at central lab). See Section 4.1 for details.
- b An abbreviated informed consent form will be signed at Screening visit.
- c Enrolment visit will occur 7 days (+3 days) after patient provides signed abbreviated screening Informed Consent form. However patient can be enrolled as soon as laboratory screening results for HbA1c are available and it is determined that the value meets the inclusion/exclusion criteria.
- d Visit 2 (Randomisation/Baseline) should be performed 14 days (±3 days) after Enrolment visit, when laboratory results from Visit 1 are available.
- e Once a patient is randomised at Visit 2, all subsequent visits should be scheduled relative to Visit 2.
- f Brief physical examination could be performed at visit 2,3 and 4 at Investigators discretion
- g Review of concomitant medications includes over the counter drugs and herbal/nutritional therapies.
- h Urine HCG pregnancy test for WOCBP (performed at site by dipsticks provided by central laboratory) at Visit 1 and 2. In case of suspected pregnancy, home pregnancy testing should be performed after randomization

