#### i CC

- j Re-testing of HbA1c at central laboratory is permitted once within one month of the initial screening visit if central laboratory result of HbA1c is >7.0% and <7.5% or >10% and <10.5%.
- k For rescued patients, rescue medication should also be returned at Visit 4 and 5.

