## 4.3.2 Treatment period visits (Visits 3 and 4; Weeks 6 and 12)

Prior to these visits, patients are required to have fasted overnight (8 to12 hours). Patients are advised to refrain from alcohol intake and intense exercise 24 hours prior to each visit and recommend not to use tobacco/nicotine within 12 hours prior to each visit. Patients should delay administering their morning dose of metformin and study medication on the morning of the study site visits. Patients should bring their metformin and study medication with them to the study site and will self-administer study medication as directed by study-site personnel.

The following will be performed during these visits:

- 1. A brief physical examination may be conducted at Investigators discretion (see Section 5.2.2).
- 2. Vital signs (sitting systolic and diastolic BP and Heart Rate) will be measured (see Section 5.2.3).
- 3. Body weight will be measured Section 5.1.3.
- 4. Concomitant medications (including over the counter and herbal/nutritional supplements) will be reviewed.
- 5. Blood samples will be collected prior to administration of study medication for the following assessments:
  - Clinical chemistry (see Section 5.2.1)
  - Hematology except Visit 3 (see Section 5.2.1)
  - HbA1c
  - eGFR (MDRD)
  - FPG (samples for central laboratory testing, see Section 5.2.1
- 6. Urine will be collected for urinalysis.
- 7. AEs and SAEs will be reviewed.
- 8. Patient diary will be reviewed for glucometer values and/or hypoglycaemic events history

- 9. Diet and Exercise counseling will be provided.
- 10. Glucose meter and/or supplies and instructions will be provided.
- 11. Patient diary and instructions will be provided.
- 12. Study medication will be dispensed and returned (except Visit 3). Study site personnel will monitor administration of study medication and morning dose of metformin with food.
- 13. Study medication compliance will be reviewed
- 14. Rescue medication will be dispensed (as necessary, see Table 1)

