## 4.4 Rescue therapy

During the double-blind treatment period of the trial, patients may be eligible for treatment with open-label rescue medication (see Table 6) to replace their blinded treatment regimen in order to treat ongoing hyperglycaemia. The sub-sections and table listed below define the lack of glycaemic control criteria for initiation of rescue medication.

Pre-specified glycaemic criteria (see Table 2), based upon repeat confirmatory central laboratory FPG have been established during the double-blind treatment period, starting at

Table 2 Criteria for Initiation of Rescue Therapy During the Randomised Treatment Period

Visit Period	Central Laboratory glycaemic parameters		
At Week 6	FPG >270mg/dL (15.0mmol/L)		
From Week 6 to Week 12 (Excluding Week 12)	FPG > 240 mg/dL (13.3 mmol/L)		
Week 12 to Week 24	FPG > 200mg/dL (11.1mmol/L)		

Week 6, to determine eligibility for open-label rescue medication.

Abbreviations: FPG Fasting plasma glucose

Patients with a central laboratory FPG value meeting the lack of glycaemic control criterion at a pre-specified visit will be scheduled for a follow-up visit (within 3 to 5 days) to obtain a second central laboratory FPG value and review the patients glucose meter readings. If the repeat central laboratory FPG value still meets the criterion, the patient must be rescued.

Patients who meet rescue criteria in the double-blind treatment period must first complete the Rescue Visit procedures before receiving open-label rescue medication to ensure that important trial endpoint measurements are collected.

Following completion of the Rescue Visit, rescued patients will be given open-label antidiabetic rescue medication (Saxagliptin 5mg and Dapagliflozin 10 mg as a first line or Insulin as a second line at Investigators discretion) and will discontinue study medication. Rescued patients will then continue in the double-blind treatment period according to their original visit schedule.

Note: Rescue medication (Saxagliptin 5mg and Dapagliflozin 10mg) will be provided by Sponsor in this study. Insulin will not be provided by Sponsor since it is part of patients standard of care.

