# 7.9.2 Open label Rescue Medications

Patients may be eligible for rescue therapy (see Section 4.4) with open-label rescue medication (Saxagliptin 5mg and Dapagliflozin 10mg as a first line therapy) in order to treat ongoing hyperglycaemia. Patients should stop receiving blinded study medication while receiving rescue therapy. If rescue therapy fails, sufficient therapy will be given at the discretion of the Investigator.

Rescue medication (Saxagliptin 5mg and dapagliflozin 10mg) will be provided by the sponsor. However, insulin will not be provided by the Sponsor, since it is part of patient's standard of care.

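### Section 4.5 item 13 waives return of the blinded tablets at the Rescue Visit, the visit at which the patient must stop them and is given rescue tablets of the same colour and shape

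*Protocol*

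**What the plan says.** - **Stopping.** Protocol 4.4 sets out the rescue options and the stop rule together: "Insulin as a second line at Investigators discretion) and will discontinue study medication". Section 7.9.2 repeats the rule: "Patients should stop receiving blinded study medication while receiving rescue therapy".
- **Order of events.** Under 4.4 the Rescue Visit procedures come first and the rescue tablets are given after them.
- **Table 1.** The row for return of study medication is marked at Visit 4 and in the Visit 5 column, headed "End of Treatment / Early Termination/ Rescue Fasting". The Notes entry for that row points to Section 4.5.
- **Section 4.5.** This section governs the Rescue Visit as well as Visit 5. Patients are told to "bring metformin and study medication to the study site visit". Item 13 then says "Study medication will be returned (not applicable for rescue visit".
- **Other returns.** Section 4.3.2 item 12, on Visits 3 and 4, says "Study medication will be dispensed and returned (except Visit 3". Table 1 footnote k adds "For rescued patients, rescue medication should also be returned at Visit 4 and 5".
- **Discontinuation in general.** Section 3.9.4 says "patient diaries and all study drugs should be returned by the patient". That sentence concerns a patient who decides to stop, so for rescue it shows intent only.
- **Appearance.** Tables 5 and 6 describe dapagliflozin 5 mg, its placebo and the 10 mg rescue tablet alike: green, plain, diamond-shaped, film-coated. Saxagliptin 5 mg, its placebo and the rescue tablet are all yellow, plain, biconvex, round and film-coated. Neither table gives a size.

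**The concern.** The mark in Table 1 and the section it points to disagree, and the section's version is the less safe one. No text tells the patient to keep the bottles, and a site may still collect them. But a site that follows item 13 sends home a supply the patient has just been told to stop, alongside a new supply that looks the same by description.

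Two errors become possible. A patient who takes both supplies exceeds the intended dose of both drugs in the combination arm and of one drug in each single-agent arm. A patient who takes only the old supply stays on the treatment that failed.

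There is also a smaller data point. Section 7.6 bases compliance on a tablet count when medication is returned, and item 13 removes that count at the visit where blinded treatment ends.

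**Working it through.** The plan states no figure on this point, so there is nothing to reproduce. The check covers the time to the next return, the doses, and the compliance formula.

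**Time from rescue to the next scheduled return.** Table 1 sets Visits 3, 4 and 5 at days 42, 84 and 168, each ±7 days. Section 4.4 requires a repeat central-laboratory FPG within 3 to 5 days. Visit 3 has no return, so the next return is Visit 4 after a Week 6 trigger and Visit 5 after a Week 12 trigger. Rescue is first placed on the day of the repeat test.

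| | Week 6 trigger | Week 12 trigger |
|---|---|---|
| Rescue day, nominal | 42 + 3 to 5 = 45 to 47 | 84 + 3 to 5 = 87 to 89 |
| Days to return, nominal | 84 − 47 = 37 to 84 − 45 = 39 | 168 − 89 = 79 to 168 − 87 = 81 |
| Shortest, with windows | (84 − 7) − (42 + 7 + 5) = 23 | (168 − 7) − (84 + 7 + 5) = 65 |
| Longest, with windows | (84 + 7) − (42 − 7 + 3) = 53 | (168 + 7) − (84 − 7 + 3) = 95 |

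Rescue must wait for the repeat result. If that takes 0 to 7 days (an assumption), the nominal ranges become 30 to 39 days (37 − 7 = 30) and 72 to 81 days (79 − 7 = 72). With both the windows and a 7-day delay, the shortest intervals are 23 − 7 = 16 and 65 − 7 = 58 days.

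**Tablets still in hand.** Table 1 dispenses study medication at Visits 2 and 4, and 7.2 sets two tablets a day. Pack size is not stated. If each dispensing covers 84 days, that is 168 tablets.

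- Rescue on day 45 to 47 leaves 168 − 90 = 78 down to 168 − 94 = 74 tablets.
- Rescue 3 to 5 days after Visit 4 leaves 168 − 6 = 162 down to 168 − 10 = 158, nearly the whole second supply.

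**Daily dose if both supplies are taken.**

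| Arm | Dapagliflozin | Saxagliptin |
|---|---|---|
| Combination | 5 + 10 = 15 mg | 5 + 5 = 10 mg |
| Dapagliflozin | 5 + 10 = 15 mg | 0 + 5 = 5 mg |
| Saxagliptin | 0 + 10 = 10 mg | 5 + 5 = 10 mg |

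The intended rescue dose is dapagliflozin 10 mg and saxagliptin 5 mg.

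**Patients.** The documents give no rescue rate. Each 1% of 900 patients rescued is 9 patients.

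**Compliance.** SAP 4.2.3.3 counts tablets taken as dispensed minus returned, divided by planned tablets. Tablets returned at Visit 4 or 5 are subtracted correctly, so the problem is mainly lost tablets. For rescue on day 88, planned tablets are 88 × 2 = 176.

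- End date equal to the rescue date: 35 lost tablets give (176 + 35)/176 = 119.9%, and 36 give (176 + 36)/176 = 120.5%. So 36 must be lost to pass the 120% limit in SAP Table 1, deviation 6.
- Tablets taken for 18 more days and end date equal to the last dose: (106 × 2)/(106 × 2) = 212/212 = 100%. The formula then does not show that the stop rule was broken.

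This reaches only the per protocol set. Its analysis is dropped if fewer than 10% of patients have relevant deviations (SAP 2.2), and it already excludes data after rescue (SAP 4.2.4.1, Sensitivity analysis).

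**The case against.** **A general mark with a specific exception.** The Table 1 column serves three kinds of visit, and its note sends the reader to 4.5, which states an exception for one of them. Section 4.5 qualifies another mark in that column, since item 1 makes the physical examination discretionary, and item 12 has a similar rescue exemption for the diary. This weakens the charge of plain contradiction. It does not supply a reason for the exemption. The diary exemption is sensible because a rescued patient stays in the study and still needs a diary; the patient no longer needs the stopped tablets.

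**Return is deferred.** The word *also* in footnote k suggests that leftover blinded tablets come back with rescue tablets at Visit 4 or 5. That is a fair reading, but it still leaves both supplies at home for the intervals above.

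**Section 3.9.4.** Anyone who discontinues study medication has an Early Termination Visit equivalent to Visit 5, and item 13 does not exempt that visit. A rescued patient also discontinues study medication, so a site has grounds to collect the bottles, as it does under the accountability rules in 7.7. This stands as mitigation, but it gives the site two opposing instructions for one patient.

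**The harm is conditional.** It needs a site that does not collect and a patient who does not follow the instruction to stop. Labels carry directions for use (7.4), tablets are taken from separate bottles (7.2), and 6.5 provides for overdose reporting. Section 1.3 also notes that saxagliptin was studied at 2.5 to 10 mg. All of this stands. These safeguards lower the risk without removing the stopped supply, and dapagliflozin 15 mg is above the 10 mg step-up dose in 1.1.

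**Conclusion.** The concern holds. Item 13 exempts from return the patients who must stop the blinded tablets and who are then given tablets of the same described colour and shape. The rule as written gives a worse result than its deletion would, under either reading of Table 1 and footnote k.

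The size is an exposure window of about five to twelve weeks on nominal days, or 16 to 95 days across the visit windows and an assumed result delay of up to 7 days. Within it, a double dose of up to dapagliflozin 15 mg and saxagliptin 10 mg a day is possible. How often that would happen cannot be derived from the documents. The likeness rests on table descriptions without size, and nothing prevents a site from collecting the tablets, so the claim is that they can go home, not that they will.

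The effect on compliance is minor and the primary analysis is unaffected. The change should be made on grounds of patient safety and drug accountability.

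**What to change.** Delete the parenthesis in Section 4.5 item 13, so that return applies at the Rescue Visit as Table 1 already indicates. Add that the blinded bottles are collected and counted at that visit before any rescue tablets are dispensed. Keep footnote k for the return of rescue medication at Visits 4 and 5.

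The cost is a changed line in 4.5 and a reminder to sites. No visit is added, because the patient is on site and has already been told to bring the study medication. The SAP needs no change.

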## 5. STUDY ASSESSMENTS

A Web Based Data Capture (WBDC) system will be used for data collection and query handling. The Investigator will ensure that data are recorded on the eCRFs as specified in the Clinical Study Protocol (CSP) and in accordance with the instructions provided.

The Investigator ensures the accuracy, completeness, and timeliness of the data recorded and of the provision of answers to data queries according to the Clinical Study Agreement (CSA).

The Investigator will sign the completed eCRFs. A copy of the completed eCRFs will be archived at the study site.

## 5.1 Efficacy assessments

Study outcome measures are summarised in Section 8.4

## 5.1.1 HbA1c

Blood samples for measurement of HbA1c will be collected according to the schedule presented in the Study Plan (Table 1). The instructions for collection, processing, packaging, and shipping of the samples will be detailed in the laboratory manual.

The results from baseline and onwards will not be reported to the Investigator.

## 5.1.2 Fasting plasma glucose

Blood samples for measurement of FPG will be collected according to the schedule presented in the Study Plan (Table 1). The instructions for collection, processing, packaging and shipping of the samples to central laboratory will be detailed in the laboratory manual.

The results from baseline and onwards will not be reported to the Investigator unless the values meet the defined rescue criteria. In addition, if rescue medication is initiated, the central laboratory FPG value will be reported to the Investigator to ensure proper follow-up of the rescued patient.

## 5.1.3 Body weight

Body weight will be measured according to the schedule presented in the Study Plan (Table 1). The study site staff should use a digital precision scale if possible, and record the weight in kilograms to the first decimal point (e.g., 95.3kg). The same scale should be used and the patient should wear a standard hospital-type gown or equivalent light clothing and no shoes for the body weight measurement at each visit.

#### 5.1.4 Body height

Body height will be measured according to the schedule presented in the Study Plan (Table 1). The study site staff should record the height in centimetres. The patient should remove their footwear and head gear and stand with feet together, heels against the back board, and knees straight.

## 5.2 Safety assessments

The Investigator will evaluate all Screening, Enrolment and safety laboratory reports and will sign and date the review. Any out of range laboratory results should be assessed for clinical significance and reported as AEs accordingly. The Investigator should follow all clinically significant laboratory abnormalities occurring during the study that were not present at baseline. These abnormalities should be evaluated with additional tests, if necessary, until the underlying cause is diagnosed or resolution occurs. The diagnosis and resolution date must be reported to the Sponsor.

Samples will be collected according to the schedules presented in the Study Plan (Table 1), the instructions for collection, processing, packaging, and shipping of the samples will be detailed in the laboratory manual.

#### 5.2.1 Laboratory safety assessments

Blood and urine samples for determination of clinical chemistry, haematology, and urinalysis will be taken at the times indicated in the Study Plan (Table 1).

The date and time of sampling will be recorded on the laboratory requisition form. The instructions for collection, processing, packaging, and shipping of the samples will be detailed in the laboratory manual.

Additional safety samples may be collected if clinically indicated at the discretion of the Investigator.

The Investigator should make an assessment of the available results with regard to clinically relevant abnormalities. The laboratory results should be signed and dated and retained at center as source data for laboratory variables. For information on how AEs based on laboratory tests should be recorded and reported, see Section 6.3.5

